| 2. | Medical condition or illness, which in the opinion of the research psychiatrist, would interfere with the patient's ability to participate in the trial. |
| 3. | Physical dependence on substances (alcohol or illicit drugs) likely to lead to withdrawal reaction during the course of the study in the clinical opinion of the treated research psychiatrist. |
| 4. | Immediate risk of harm to self or others. |
| 5. | Female who is currently pregnant or breastfeeding. |

Study Design

The project will be implemented as a prospective 12-week RCT of CAE-S vs. enhanced treatment as usual (eTAU) in 36 poorly adherent individuals with schizophrenia. Patients with schizophrenia will be randomly assigned to receive either CAE-S or eTAU following the baseline assessment. The primary feasibility outcomes will be attendance and patient satisfaction (Aim 1) and change from baseline to 12 weeks in schizophrenia symptoms as measured by the Positive and Negative Symptom Scale (PANSS) (Aim 2). An exploratory evaluation (Aim 3) will examine the posited mechanistic underpinnings of the CAE-S intervention by assessing change from screening to 12 weeks in psychotropic medication adherence as measured by the Tablets Routine Questionnaire (TRQ) and validated by eCAP (objective bottle openings). Secondary measures will include the Clinical Global Impression (CGI), functional status, quality of life and attitudes towards medication. Findings will be summarized in at least one manuscript submitted for peer-reviewed publication, paving the way for a larger-scale trial, and will help inform clinicians on care approaches which may optimize antipsychotic medication response in their patients with schizophrenia.

Customized Adherence Enhancement (CAE) Intervention: CAE is an adjunctive (to standard medication treatment) behavioral intervention delivered virtually (real-time one on one video-conferencing) in 6 individual sessions. Because the CAE manual does not target any specific oral antipsychotic medication or group of antipsychotic medications, (it is unbranded) positive

findings from the proposed trial will enhance potential usability across a broad variety of oral antipsychotic medications.

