Statistical Analysis: Our study proposes to assess the primary outcome of change from baseline to week 12 on the PANSS. Expected magnitude of change is informed by results of 2 previous studies using CAE in schizophrenia by these PIs ([name] 2013, [name] 2017). We will conduct descriptive analysis of baseline variables (i.e., age, gender, ethnicity, and level of education). The PANSS total will be a sum of global symptoms of schizophrenia. First, we will compare the changes in PANSS from baseline to 12 weeks, respectively, for the CAE-S and eTAU groups using a non-parametric Wilcoxon rank-sum test to determine whether the subgroup medians differ. Should baseline-covariates differ between subgroups, we will conduct the appropriate multivariable linear regression for normalized outcome measures, to account for residual confounding. Analysis of the secondary outcomes will be conducted in a similar manner. An intent-to-treat analysis will be conducted. We will assess the missing at random assumption for the mixed models for missing data due to dropout or missed assessments.

We project a sample size of 36 subjects, randomized in equal numbers (CAE=18, eTAU= 18). In our previous study using CAE and long-acting injectable antipsychotic medication in homeless individuals with schizophrenia, 10 (33%) out of 30 subjects dropped out after 24

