weeks, including 3 (10%) due to incarceration (thus, 23% due to other discontinuation reasons). This study will not specifically enroll homeless individuals, but rather those who are on oral antipsychotics prescribed by the patient's outpatient clinician; thus, we believe the attrition proportion will be substantially smaller for the proposed study. Additionally, since the duration of observation in the proposed study is 12 rather than 24 weeks, this is expected to optimize study retention. Nonetheless, for the power calculation we hypothesize an attrition of up to 23% (N=8), a one-sided alpha of 0.05 (because we hypothesize CAE will result in improvements based on our pilot studies) For PANSS, we previously observed an average decrease in the composite score from baseline of 6.7 (SD = 7.1), there is 77% power for a sample size of 28. Thus the sample size of 36 individuals enrolled is appropriate for this conservative estimate of attrition. For our exploratory aim, adherence is calculated as a percentage of self-reported proportion of oral medications missed. Automated pill monitoring (eCAPS) will be used to validate the TRQ and we expect that CAE will improve adherence at week 12 from screen at least as comparably as it did in our study of homeless individuals⁷ (average TRQ improvement past week = 37%; SD = 36.9%). For a Wilcoxon rank-sum test, we expect there will be minimal change in adherence in the eTAU group at week 12 – for which we have 81% power to detect a difference; even if the eTAU group reports a 5% change, there is still 71% power to detect a difference.

Risks to Research Participants

Any time information is collected, there is a potential risk for loss of confidentiality. There are no other known risks of harms or discomforts associated with this study beyond those encountered in normal daily life. Some of the activities we will ask you to complete might make you feel uncomfortable or tired. Participants may refuse to answer any of the questions, take a break, or stop your participation in this study at any time.

Provisions to Protect the Privacy Interests of Research Participants

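### The primary rank-sum test on PANSS change is described as a test of medians, which it is not without an equal-shape assumption, and no unconditional PANSS-point estimate or interval is prespecified

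*Combined protocol and SAP*

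**What the plan says.** The Data Analysis Plan names its primary endpoint as follows: "Our study proposes to assess the primary outcome of change from baseline to week 12 on the PANSS". The two arms are compared "using a non-parametric Wilcoxon rank-sum test to determine whether the subgroup medians differ", and the secondary outcomes are to be handled in the same way. No assumption about the shapes of the two distributions is stated.

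Two other analyses are mentioned:

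- A regression that depends on what is seen at baseline: "Should baseline-covariates differ between subgroups, we will conduct the appropriate multivariable linear regression for normalized outcome measures, to account for residual confounding". The meaning of normalized is not given.
- Mixed models, which appear only in the sentence on missing data: "We will assess the missing at random assumption for the mixed models for missing data due to dropout or missed assessments". No model, contrast or estimate is specified.

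No mean difference, median difference, shift estimate, standardized effect or confidence interval is named anywhere. The sample size, by contrast, rests on a mean and SD in PANSS points, an "average decrease in the composite score from baseline of 6.7 (SD = 7.1"). The Objectives include preliminary efficacy, and the Study Design section describes the results as "paving the way for a larger-scale trial".

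**The concern.** The rank-sum test responds to the probability that a CAE-S patient's change is lower than an eTAU patient's. That becomes a statement about medians only if one distribution is the other moved sideways. An adherence intervention may well break that condition: some patients could improve a good deal while others hardly move, which skews one arm and not the other. The test can then reject although the medians are equal, and the plan's wording would turn that rejection into a claim about medians.

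The second part is what the pilot commits to deliver. A larger trial has to be planned on the size of the PANSS difference, its uncertainty and the SD of change. A p-value gives none of these, and the plan promises nothing else unconditionally. Both parts carry over to the secondary outcomes.

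**Working it through.** **Inputs from the Data Analysis Plan.** 36 patients randomized 18 + 18; attrition up to 23% (8 patients), leaving 28; one-sided alpha 0.05 for the power calculation; difference 6.7, SD 7.1; stated power 77%. I assume the 28 completers split 14 + 14.

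**Step 1: the plan's own figure.** The standardized difference is d = 6.7 / 7.1 = 0.944. The Wilcoxon efficiency for normal data, 3/π, gives an effective 14 × 3/π = 13.37 per arm and a noncentrality of 0.944 × √(13.37/2) = 2.44. The one-sided noncentral t power is 76.6%, which matches the stated 77%. This requires taking the earlier decrease from baseline as the between-arm difference, with no eTAU change and a common SD. I do not dispute the 77% here.

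**Step 2: does a rejection imply different medians?** Simulated rank-sum test, one-sided 5%, true median 0 in both arms. The shapes are my assumptions. Unless noted, eTAU change is normal with SD 7.1.

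| CAE-S change (lower is better) | 14 per arm | 18 per arm |
|---|---|---|
| Same normal as eTAU | 4.8% | 4.8% |
| Normal, SD twice eTAU's | 5.2% | 5.5% |
| Normal, SD three times eTAU's | 5.9% | 6.1% |
| Exponential tail toward improvement, SD 7.1 | 12.0% | 14.3% |
| Two-piece normal, scale 10 on the improving side and 4 on the other | 14.4% | 17.5% |

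A responder mixture behaves in the same way. Let half the CAE-S patients improve by an exponential amount with mean m, and half worsen by a half-normal amount with scale s. The mean improvement is 0.5m − 0.5 × 0.798s, and the mean square is m² + 0.5s².

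- m = 7, s = 3: mean 3.5 − 1.2 = 2.3; SD = √(49 + 4.5 − 2.3²) = 6.9; rejection about 14% at 14 per arm.
- m = 7.7, s = 1.54: mean 3.85 − 0.61 = 3.2; SD = √(59.3 + 1.2 − 3.24²) = 7.1; rejection about 23% at 14 per arm.

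Differing skew drives the effect; differing spread alone adds little. At two-sided 5% the rates are lower: 7.1% for the exponential tail and 8.6% for the two-piece normal at 14 per arm.

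**Step 3: the interval the pilot could report.** SE = 7.1 × √(2/n); half-width = t × SE with 2n − 2 degrees of freedom.

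- n = 14: SE = 2.68; 2.056 × 2.68 = ±5.5 points. An observed 6.7 would give 1.2 to 12.2.
- n = 18: SE = 2.37; 2.032 × 2.37 = ±4.8 points.

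**Step 4: why the width matters for the next trial.** For 90% power at two-sided 5% with SD 7.1, n per arm = 2 × (1.960 + 1.282)² × 7.1² / δ², or about 1,059 / δ². The total is 48 for δ = 6.7, 134 for δ = 4, 236 for δ = 3 and 1,472 for δ = 1.2. A p-value does not distinguish these.

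**The case against.** The best defence is that the sizing fits a location-shift model. Under that model the mean shift and the median shift are the same, so the reference to medians is loose wording and not a contradiction. That stands as an account of how the wording arose. It does not supply the assumption, which the plan never states for the analysis.

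Several stronger readings are tempting, and the documents do not support them.

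- *The test is invalid or inflates false positives.* It keeps its level when the arms are identical (4.8%). In the skewed cases CAE-S patients really do better on average, so a rejection detects a true difference and gives it the wrong name.
- *No effect estimate is planned at all.* The conditional regression and the mixed models could each yield a between-arm coefficient. Neither is tied to a reported estimate with an interval.
- *The regression coefficient is not in PANSS points.* The plan refers to "multivariable linear regression for normalized outcome measures" without definition. The term may mean a transformation, or only outcomes that are close to normal.
- *The larger trial will have no PANSS-point effect to use.* The Schedule of Events collects PANSS at baseline and week 12, so a difference can always be computed. What is missing is the commitment.
- *A non-significant result will be read as no effect.* No sentence says so.

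A more dramatic illustration is also available. With m = 15 and s = 3 the mean difference is 6.3 points and the test rejects about 26% of the time. But the CAE-S SD is then √(225 + 4.5 − 6.3²) = 13.8, nearly twice the plan's 7.1, so I do not rely on it.

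**Conclusion.** The stated interpretation of the primary test is wrong as written, and the matching reporting commitment is missing. Severity is minor. At an SD near the plan's own value, with equal medians and 14 per arm, the illustrative responder mixtures give 14% to 23% rejection at one-sided 5%. Those rates rest on assumed shapes and are not bounds: the exponential tail gives 12%, and a difference in spread alone gives 5% to 6%. One-sided testing follows the power calculation; the plan does not state sidedness for the analysis itself. The interval half-widths of 5.5 and 4.8 points assume that the SD of 7.1 from earlier work applies to both arms.

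**What to change.** 1. Remove the statement that the test determines whether medians differ. Say instead that it tests whether PANSS changes in one arm tend to be lower than in the other.
2. Report for PANSS, whatever the baseline balance or the p-value, the between-arm difference in mean change in raw points with a 95% interval, and the SD of change in each arm. Do the same for the secondary outcomes on their raw scales.
3. Define normalized in the regression sentence, and either specify the mixed models or remove the reference.
4. A Hodges-Lehmann estimate is optional. If given, label it as assuming a common shape, since it rests on the same condition that is in doubt here.

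The cost is a few lines of plan text and analysis code. No new data are needed, and the stated 77% power is unchanged.

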Enhanced Treatment as Usual (eTAU): Individuals in eTAU will receive an eCAP for their foundational antipsychotic medication and continue to receive care, including prescribed antipsychotic medication with their current non-study providers. Medication adherence behavior typically transiently improves during early phases of focused monitoring (Hawthorne effect), but this wanes over time¹⁶ with expected regression to behaviors existing prior to study enrollment unless otherwise reinforced with an approach like CAE. To optimize control intervention rigor, the eTAU participants will view a pre-taped series of videos (based on NAMI or DBSA general wellness guidelines) 1:1 with a therapist who has similar credentials and competency as the CAE mental health clinician during 6 one-on-one sessions lasting at least approximately 30 minutes. The therapist will view the videos with the participant and field questions the patient may have. This controls for attentional effects, an important consideration in behavioral clinical trials. As an additional consideration to optimize rigor, while study staff are not blinded to intervention assignment, outcomes assessments are collected by non-interventionist research staff, and outcomes data analysts are blinded to the nature of intervention assignment.

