Alcohol and Substance Use: The Alcohol, Smoking and Substance Involvement Screening Test (ASSIST) is a widely used and validated 8-item measure of alcohol and drug use (World Health Organization ASSIST Working Group, 2002).³³

Quality of Life (QoL): The Short Form Health Survey (SF-12) will be used to assess health related quality of life.³⁴ This 12-item self-report Health-related Quality of Life measure has an index for mental health and an index for physical health and has been validated in individuals with serious mental illness.³⁵

[figure not shown]
Schedule of Events

| | Screen | Baseline (~1 week after screen) | Weeks 2-8 | 12 weeks |
|---|--------|------------------------------------|-----------|----------|
| Screening, Informed consent | X | | | |
| Inclusion/Exclusion | X | | | |
| Demographics | X | | | |
| Diagnostic Interview (MINI) | X | | | |
| Medical burden (Charlson) | X | | | |
| Randomization | | X | | |
| eCAP administration and training | X | | | |
| Primary Outcome: Schizophrenia Symptoms - PANSS | | X | | X |
| Secondary outcomes: Adherence Behavior: TRQ, directly-observed pill counts and eCAP* | X | X | | X |
| Secondary outcomes: | | X | | X |

| | | | |
|---------------------------------------|--|--|----------|
| Adherence Attitudes: DAI, PROMIS | | | |
| Global Psychopathology: CGI | | | |
| Social Functioning: Strauss-Carpenter | | | |
| Alcohol/Substance Use: ASSIST | | | |
| Quality of Life: SF-12 | | | |
| Health Resource Use | | | |
| CAE sessions/attendance | | | X |
| ETAU sessions/attendance | | | |
| Participant satisfaction | | | X |

*eCAP data collection will start at baseline following distribution at screen

Figure 1: Study Design

Data Analysis Plan

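### The leading PANSS test subtracts baseline PANSS without adjusting for it, and an undefined imbalance trigger decides whether an adjusted analysis is run, with no statement of which result governs

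*Combined protocol and SAP*

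**What the plan says.** The statistical analysis paragraph of the Data Analysis Plan sets the order: "First, we will compare the changes in PANSS from baseline to 12 weeks, respectively, for the CAE-S and eTAU groups", by a Wilcoxon rank-sum test. Baseline PANSS enters only by subtraction. The second step is conditional: "Should baseline-covariates differ between subgroups, we will conduct the appropriate multivariable linear regression for normalized outcome measures, to account for residual confounding". The only baseline variables named in that paragraph are age, gender, ethnicity and education, and they are listed for description. For other endpoints it says "Analysis of the secondary outcomes will be conducted in a similar manner". Mixed models are mentioned once, in connection with missing data, with no model terms.

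Elsewhere:
- Study Design has patients "randomly assigned to receive either CAE-S or eTAU following the baseline assessment", and the Schedule of Events row "Primary Outcome: Schizophrenia Symptoms - PANSS" is marked at baseline and at 12 weeks. A pre-randomisation PANSS is therefore planned for everyone.
- Study Design describes the adherence analysis as "assessing change from screening to 12 weeks in psychotropic medication adherence", and the sample-size text also measures TRQ change from screen.
- The Schedule of Events footnote says "eCAP data collection will start at baseline following distribution at screen".
- The eTAU section says "outcomes data analysts are blinded to the nature of intervention assignment".

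**The concern.** There are two linked gaps.

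First, subtracting a baseline is not the same as adjusting for it. Change still depends on the baseline value unless the slope of week-12 PANSS on baseline PANSS is 1. At any other slope, a chance baseline difference between two small arms moves the Wilcoxon comparison.

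Second, the route to an adjusted analysis has no working definition. Nothing says which covariates are examined, how large a difference counts, or whether baseline PANSS is among them. The stated reason, residual confounding, does not fit a randomised comparison. Among all 36 randomised patients a baseline difference is chance; among completers it may also reflect dropout. The word *First* suggests that the Wilcoxon test leads, but the plan does not say what happens if the regression disagrees, or how the mixed models relate to either. The similar-manner sentence carries the same gap to every secondary outcome.

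At stake are some power, some protection against an unlucky allocation, and a clear answer to which p-value decides the PANSS hypothesis.

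**Working it through.** **Inputs from the sample-size text.** Decrease 6.7, SD of change 7.1, one-sided alpha 0.05, 36 randomised 1:1, up to 8 lost. 36 − 8 = 28, taken as 14 per arm. No change is assumed under eTAU.

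**The plan's own figure.** Noncentrality = 6.7 / (7.1 × √(2/14)) = 2.50; a one-sided t-test with 26 df has 78.4% power. With the Wilcoxon efficiency 3/π, the effective size is 14 × 0.955 = 13.4 per arm and power is 76.6%. The stated 77% reproduces, as the power of the *unadjusted* test.

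**Assumptions not in the documents.** The baseline to week-12 correlation ρ, and the ratio k of week-12 SD to baseline SD. The SD of change is held at 7.1, so baseline SD = 7.1 / √(1 + k² − 2ρk). The slope of week 12 on baseline is ρk.

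**Average power** (normal data, k = 1, simulation of 40,000 trials per setting, exact Wilcoxon):

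| ρ | 0.5 | 0.7 | 0.85 | 0.9 |
|---|---|---|---|---|
| Wilcoxon on change | 75% | 75% | 75% | 75% |
| Rank of change on arm and rank of baseline (rank ANCOVA) | 84% | 80% | 77% | 76% |
| Linear ANCOVA | 87% | 82% | 79% | 79% |

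Part of the rank ANCOVA gap arises because the exact Wilcoxon test attains size 0.0469, not 0.05. At matched size the gain is about 7.5 / 4 / 1 / 0 points.

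The gain also moves with k. At k = 0.9 it is about 6 to 12 points. At k = 1.11 to 1.2 it runs from about 6 points to nil, and is absent at correlations of 0.85 and above.

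Linear ANCOVA is not uniformly better. With lognormal residuals (k = 1) it has 89 / 87 / 85 / 85% against 93 / 96 / 97 / 98% for the Wilcoxon test. With t(3) residuals it falls below the Wilcoxon test from ρ = 0.7 upwards.

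**Chance imbalance of exactly 1 SE** (k = 1). One SE = baseline SD × √(2/14). The shift in the mean change difference is (1 − ρk) × imbalance.

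| ρ | 0.5 | 0.7 | 0.85 | 0.9 |
|---|---|---|---|---|
| Baseline SD | 7.1 | 9.2 | 13.0 | 15.9 |
| 1 SE, PANSS points | 2.7 | 3.5 | 4.9 | 6.0 |
| Shift, PANSS points | 1.3 | 1.0 | 0.7 | 0.6 |
| Wilcoxon power, CAE-S lower | 60% | 64% | 67% | 68% |
| Wilcoxon power, CAE-S higher | 91% | 87% | 83% | 82% |
| Wilcoxon rejection under the null, CAE-S higher | 8.4% | 7.8% | 7.2% | 6.8% |
| Wilcoxon rejection under the null, CAE-S lower | 0.7% | 1.5% | 2.3% | 2.7% |

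Rank ANCOVA stays between about 76% and 85% power in both directions, and near 5% under the null. An imbalance of at least 1 SE arises in about 16% of trials in each direction. The two directions offset: overall null rejection of the Wilcoxon test is 4.5 to 4.9%.

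This effect depends on the slope. At ρ = 0.9 and k = 1.11 the slope is 0.9 × 1.11 = 1.0, the shift is zero, and with CAE-S 1 SE lower both tests have about 75 to 76% power. At ρ = 0.9 and k = 1.2 the slope is 1.08 and the direction reverses: the Wilcoxon test then has about 80% against about 76%.

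**Two results, no hierarchy** (k = 1). If the regression were run in every trial with baseline PANSS in it, it and the Wilcoxon test would disagree in about 16 / 12 / 10 / 9% of trials under the planned effect. If a positive result on either could be claimed, type I error would be about 6 to 7%.

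**How often might the trigger fire?** The plan gives no rule. As an illustration, suppose it means a p-value below a threshold on any of the four named variables, taken as independent. By chance it fires in 1 − 0.95⁴ = 18.5% of trials at 0.05, and in 1 − 0.90⁴ = 34.4% at 0.10. Such a trigger says nothing about balance on PANSS itself.

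**The case against.** The strongest reply is that the planned test is sound and this is a wording matter. It is valid under randomisation and its power reproduces. Outcomes data analysts are blinded, the trigger looks only at baseline data, and the trial seeks preliminary efficacy. One sentence saying that the Wilcoxon test governs would remove the ambiguity without a new model. The four named variables are natural candidates for the covariate list. The choice of a rank-based adjusted test is partly preference. All of this stands. It does not supply a definition of the trigger or a governing result, and a sentence favouring the Wilcoxon test would leave the available baseline information unused.

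Several stronger readings are tempting, and the documents do not support them:
- *The primary test has inflated type I error.* It does not on average. Excess rejection when CAE-S starts higher is offset when it starts lower.
- *Adjustment is sure to raise power, or at least always protects against imbalance.* Both depend on the unknown correlation and SD ratio. The average gain can be nil, and the imbalance effect vanishes at slope 1.
- *One trial in ten will give conflicting verdicts.* The 9 to 16% assumes that the regression is always run and contains baseline PANSS. The plan commits to neither, so the actual rate depends on how often the undefined trigger fires.
- *Analysts will choose the favourable result.* Nothing suggests this, and the blinding limits it.

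**Conclusion.** The point holds and should be corrected before analysis. It does not invalidate the trial. The wording gap is certain: no committed adjustment for baseline PANSS, no definition of the trigger, and no ranking of the Wilcoxon test, the regression and the mixed models.

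Its numerical size is conditional. At 14 per arm with normal data and equal SDs, always adjusting by ranks gains roughly 9 points of average power at a correlation of 0.5, falling to about 1 point at 0.9. Other SD ratios give anything from about 12 points to nil. A 1-SE baseline imbalance can move Wilcoxon power appreciably either way when the slope is well below 1, and has no effect when the slope is 1. The 6 to 7% type I error applies only if either of two results, both always available, may be claimed.

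**What to change.** 1. Pre-specify one governing PANSS test that always includes baseline PANSS. A regression of the rank of PANSS change on arm and rank of baseline PANSS keeps the plan's non-parametric intent. Linear ANCOVA is an acceptable alternative, with the caution that it can lose power under skewed or heavy-tailed residuals.
2. Keep the unadjusted Wilcoxon test as a sensitivity analysis.
3. Delete the imbalance trigger, or replace it with a fixed covariate list.
4. State how the governing test relates to the mixed models mentioned for missing data.
5. For secondary outcomes, adjust for the pre-randomisation value where one exists. For TRQ, use the screen value, from which the documents measure change. Leave eCAP unadjusted, because its collection starts only at baseline.
6. Label the 77% as the power of the unadjusted test.

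The cost is SAP wording and one degree of freedom. No new data are needed for PANSS or TRQ, and the sample size of 36 need not change. If the correlation proves high, the average power gain may be nil; the plan would still have a single, defined result.

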
Other outcomes of interest:

Adherence Attitudes:

The Drug Attitude Inventory (DAI), is used to measure attitudes towards medication among individuals with serious mental illness²⁶ and is known to be relatively unaffected by psychiatric symptom severity²⁷. The DAI was originally developed to assess the attitudes and subjective experience of patients with schizophrenia being treated with antipsychotic medications. The DAI is a simple, true-false format questionnaire that assesses domains of patient's attitudes including positive and negative experience, locus of control, and attitudes towards health. Responses are scored on a euphoric-dysphoric continuum (alpha= 0.93).

Patient-Reported Outcomes Measurement Information System (PROMIS) Medication Adherence Scale (PMAS)²⁸ is a 9-item self-report measure which targets the multiple potential reasons patients with various chronic health conditions may not adhere to their medications. The measure was developed using rigorous methodology²⁸ and can be used to compare to other adherence studies.

Health Resource Use: Resources that are typically utilized by the most severely ill individuals with schizophrenia include emergency care and hospitalization. Resource use in the 3-month period prior to study enrollment and during the 3-month study period will be evaluated.

Global Psychopathology: Global psychopathology will be measured with the Clinical Global Impressions (CGI)²⁹ a widely used scale which evaluates illness severity on a 1 to 7 point

continuum. Severity of illness ratings on the CGI have reported reliability scores ranging from 0.41-0.66²⁹ and correlate with the BPRS³⁰.

Social Functioning: Life and Work Functional status will be evaluated using the GAF and the Strauss-Carpenter Level of Functioning Scale (SCLFS). The GAF is a 100-point single-item scale which measures global functioning of psychiatric patients and is widely utilized in clinical studies involving Seriously Mentally Ill patients.³¹ The reliability of the GAF ranges from 0.62-0.82. Additionally we will use the SCLFS which measures functioning in four areas: symptoms in the previous month, hospitalizations, work, and social contacts in the previous year.³² Functioning in each area is rated on a scale from 0, worst functioning, to 4, best functioning.

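### Hospital and emergency use falls by default under the PANSS analysis (rank-sum on change, read as medians); if it is a sparse count, that costs power and yields no event rate or effect estimate.

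*Combined protocol and SAP*

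**What the plan says.** In the Schedule of Events, "Health Resource Use" stands in the block of secondary outcomes collected at baseline and 12 weeks. The section on other outcomes of interest describes it: "Resources that are typically utilized by the most severely ill individuals with schizophrenia include emergency care and hospitalization", and "Resource use in the 3-month period prior to study enrollment and during the 3-month study period will be evaluated".

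Under Statistical Analysis, change in PANSS is compared between arms "using a non-parametric Wilcoxon rank-sum test to determine whether the subgroup medians differ". A second step is conditional: "Should baseline-covariates differ between subgroups, we will conduct the appropriate multivariable linear regression for normalized outcome measures". The plan does not define what makes an outcome normalised. All secondary outcomes are then covered by one sentence: "Analysis of the secondary outcomes will be conducted in a similar manner".

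The Statistical Analysis text does not name resource use. The Study Design section does not list it either: "Secondary measures will include the Clinical Global Impression (CGI), functional status, quality of life and attitudes towards medication". No section says whether the variable is a number of visits, a number of days or a yes/no item. None gives an expected rate or share of zeros, and none gives it a separate method.

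**The concern.** PANSS and most of the other secondary measures are scale scores, for which a rank test on change is a reasonable default. Hospital and emergency use is different in kind. The protocol itself ties it to the most severely ill, and the inclusion criteria do not require recent use, so many patients may have none in a three-month window.

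If so, three things follow.

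- The difference between two sparse counts carries the noise of the prior count without much gain from it.
- Both arm medians of change will often be zero, so a comparison framed as one of medians has little content.
- A rank-sum p-value gives neither an event rate nor a rate ratio. Study Design says the trial should prepare a larger one, and those are the quantities its planners would want from this outcome.

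**Working it through.** **Inputs from the documents.** 36 patients, 18 per arm; attrition up to 23% (8 patients), leaving 28, or 14 per arm; one-sided alpha 0.05; PANSS change 6.7 with SD 7.1; stated power 77%.

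**The plan's own figure first.** The standardised effect is 6.7/7.1 = 0.944. The noncentrality is 0.944 × √(14/2) = 2.497. The normal approximation gives Φ(2.497 − 1.645) = 80.3%, and the noncentral t gives 78.4%. Multiplying n by the rank-sum efficiency 3/π (14 becomes 13.37) gives 76.6%. The stated 77% therefore reproduces as a one-sided rank-sum test with 14 per arm, and the same setting is used below. No corresponding figure exists for resource use.

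**Assumptions for resource use (not in the documents).** Gamma-Poisson counts in each window, with shape k = 1 and each patient's propensity shared across the two windows. The control mean m is varied. The share of zeros is (1 + m/k)^(−k), which for k = 1 is 1/(1 + m): 83% at m = 0.2, 71% at 0.4, 67% at 0.5, 56% at 0.8, 50% at 1.0.

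**Size with no effect.** In simulation the rank-sum on change rejects in 4.8% to 5.6% of trials, and an unadjusted linear model on change in 5.0% to 5.9%. Both hold close to 5%.

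**Power of the rank-sum test, on change and on study-period use** (3,000 trials per row, 14 per arm, one-sided 0.05):

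| Mean, eTAU → CAE-S | Change scores exactly zero | Equal arm medians of change | Power, change | Power, study-period use |
|---|---|---|---|---|
| 0.2 → 0.05 | 78% | 99.5% | 17% | 25% |
| 0.5 → 0.1 | 62% | 86% | 30% | 51% |
| 1.0 → 0.25 | 47% | 51% | 42% | 59% |

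**Power of the rank-sum on change against a Poisson score test adjusted for the prior count, with a permutation p-value** (2,000 trials per setting):

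| Control mean | Use halved | Use cut by 75% |
|---|---|---|
| 0.2 | 10% vs 12% | 17% vs 21% |
| 0.4 | 16% vs 21% | 23% vs 35% |
| 0.8 | 20% vs 26% | 34% vs 57% |

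The relative loss runs from (11.9 − 10.2)/11.9 = 14% to (56.8 − 34.2)/56.8 = 40%. With independent windows and use halved, the figures are 12% vs 19% (mean 0.4) and 16% vs 25% (mean 0.8). The adjusted permutation test held its size (4.8% to 5.0%).

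**Two alternatives that do not help.** Fisher's test on any use had 6% to 32% power, below the rank-sum on change in every setting with an effect. A Poisson model with robust-error Wald inference did not hold its size dependably: between about 2% and 10%, depending on the event rate and the small-sample correction. It also has no finite rate ratio when an arm has no events. For k = 1 that chance is (1/(1 + m))^14 per arm:

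- 0.5 → 0.1: 0.263 and 0.003, so 1 − 0.737 × 0.997 = 27% of trials.
- 0.2 → 0.05: 0.505 and 0.078, so 1 − 0.495 × 0.922 = 54% of trials.

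**What the trial could detect.** With 80% power at one-sided 0.05, detecting a halving of the proportion with any use needs 64 per arm starting from 40%, 157 from 20%, and 343 from 10%.

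**The case against.** The strongest reply is that the plan does not really prescribe this analysis. Statistical Analysis never names resource use, Study Design omits it from the secondary measures, and the catch-all sentence is loose. It is also true that sparseness is an assumption, that no hypothesis or power statement rests on this outcome, and that nothing bars reporting events by arm. All of this stands and limits the weight of the point. What it does not remove is that the schedule classes the outcome as secondary and no other analysis is offered, so the PANSS rule is the one in force.

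Three stronger readings are tempting, and the documents do not support them.

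- *A reader might infer that the p-value would be invalid or uninterpretable.* It would not: size stays near 5%. The loss is in efficiency and in having no estimate.
- *A reader might infer that the plan requires a linear regression that cannot be fitted.* That step applies only if baseline covariates differ and only to outcomes that are normalised. A count that cannot be normalised may be read as outside it.
- *A reader might infer that mostly-zero counts are a fact of this trial.* The documents give neither unit nor rate. They support sparseness only through the remark about the most severely ill.

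**Conclusion.** The point holds as a minor one. By default, hospital and emergency use would be analysed by a valid test that suits a sparse count poorly. Under assumed control means of 0.2 to 1.0 events per 3 months, the rank-sum on change had lower power than the same test on study-period use in every setting run. Against a test adjusted for prior use, its relative loss was about 14% to 40%. Arm medians of change coincided in about half of trials at the highest rate and in nearly all at the lowest.

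The size rests on the assumed rates, on gamma-Poisson counts and on 14 completers per arm. The direction was the same when propensity was shared across windows, when windows were independent, and with a more skewed shape of 0.5. The practical effect on this 36-patient trial is small: in the settings run, even the better methods stayed below 60% power for a 75% reduction. The larger gain is a usable event rate for planning the next trial, and a unit and model fixed in advance.

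**What to change.** In Statistical Analysis, exempt hospital and emergency use from the catch-all rule, label it exploratory, and state:

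- the unit (visits, admissions, days, or any use), with emergency and inpatient use defined separately or combined;
- by arm, the number and percentage with any use with an exact confidence interval, and events per person-month, as description rather than as a Fisher test;
- one comparison of study-period use: either adjusted for pre-enrolment use with a permutation or exact p-value rather than robust-error Wald inference, or a rank-sum test on study-period use;
- a rate ratio with confidence interval only when both arms have events, and otherwise counts and exact intervals alone.

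The cost is a few sentences and a little more analysis work on the same data. It will not make the comparison well powered: power stays low with any method at this sample size, and the report should say so.
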